1.3.2 In myocardial infarction complicated by Cardiogenic Shock non treated with VA-ECMO

There are only a few case reports and case series of hypothermia in patients with CS, mostly limited to pediatric and adult cardiac surgery patients whose postoperative courses were complicated by CS [16, 17] and none were from patients with CS in the acute MI setting. It is also important to recognize that these are reports of highly selected cases in which treatment was nonrandomized and concurrent therapy was uncontrolled. Only a well-designed randomized clinical trial can provide evidence sufficient to support clinical practice in post-MI patients.

In general, whether in infants or children, when hypothermia is added to conventional therapy in patients with refractory shock after cardiothoracic surgery, it resulted in decreases in heart rate and increases in mean arterial pressure and urine output with improved clinical stability. Therapeutic hypothermia has been reported in only three case series in adult patients with refractory heart failure.

Yahagi et al [16] reported 10 adult patients experienced post–cardiac surgery cardiogenic shock that was refractory to medical therapy, including multiple vasopressors and intra-aortic balloon pumping; the use of external cooling along with cold gastric lavage to a temperature of 34.5° C was associated with an increase in cardiac index (1.9 ± 0.3 to 2.2 ± 0.3), mixed venous saturation ($55 \pm 7\%$ to $64 \pm 6\%$), and urine output ($2.1 \pm 1.1 \text{ ml/kg/h}$ to $3.4 \pm 2.2 \text{ ml/kg/h}$) compare to baseline without changes in mean arterial pressure, heart rate, systemic vascular resistance, or pH. Eight of 10 patients survived to discharge. This study did not provided controls, but the expected mortality of patients in such condition is >50%.

Zobel et al [18] reported the effects of moderate hypothermia in 20 patients admitted in CS after resuscitation from cardiac arrest. Patients were matched with a historical normothermic group by means of propensity score. Moderate therapeutic hypothermia was associated with a significant decrease in heart rate from 74 to 64 beats per minute. Despite the reduction in heart rate, cardiac index remained unchanged under moderate therapeutic hypothermia likely due to an increase in ejection fraction from $43 \pm 4\%$ to $55 \pm 4\%$. Mean arterial pressure increased rapidly from 75 ± 2 mmHg to 84 ± 3 mmHg (p = .001) upon induction of hypothermia paralleled by an initial increase in systemic vascular resistance. Accordingly, patients with moderate therapeutic hypothermia required lower cumulative doses of vasopressors and inotropes. They concluded that in CS moderate therapeutic

hypothermia provides circulatory support and an increase in systemic vascular resistance that leads to reduced vasopressor use and may result in lower oxygen consumption.

Finally, Schmidt-Schweda [19] in 12 patients in CS found that hypothermia consistently decreased heart rate, and increased stroke volume, cardiac index and cardiac power output. Metabolic and electrocardiographic parameters remained constant during cooling.

Patients with signs of CS after cardiac arrest who underwent cooling provide another possible source of information, although little is currently available. In one study [20], 28 of 56 patients who were cooled after cardiac arrest also had CS, although it was not reported how many of these patients had acute MI concurrent with the cardiac arrest. Among the CS patients, after 24 to 48 h of therapeutic hypothermia, cardiac index increased from 1.5 ± 0.26 to 2.3 ± 0.371 . In addition, heart rate decreased among CS patients but to a lesser extent than among patients without shock; mean arterial pressure increased in patients with CS whereas it decreased in patients without initial signs of shock.

To summarize, preliminary data demonstrated that moderate hypothermia during cardiogenic shock is well tolerated and improves hemodynamic parameters.

Finally, to the best of our knowledge, there have been no published randomized human studies of therapeutic hypothermia in post-MI cardiogenic shock treated with VA-ECMO. We found only one ongoing clinical trial (NCT01890317) to test the effects of moderate hypothermia in CS following MI. Importantly, in this study, patients will not be treated with VA-ECMO.

1.4 POTENTIAL RISKS AND BENEFITS

1.4.1 Expected patient or public health benefit

Potential advantages of adding moderate hypothermia to VA-ECMO: Moderate hypothermia improves cardiac function and attenuates ischemia/reperfusion injury in other organ systems and reduces endothelial cell apoptosis and systemic oxidative stress. CS patients treated with ECMO have severe cardiac failure, associated with severe ischemia-reperfusion injury and proinflammatory profile leading to increased NO production and subsequent severe vasoplegia and multiple organs failure. Therefore, adding hypothermia in the very early phase of ECMO may alleviate the deleterious effects of ischemia-reperfusion. Moreover, moderate hypothermia is well tolerated. Finally, we intend to identify an absolute difference in the risk of death of 15%. In the field of cardiovascular medicine, the trials are usually intending to identify a 15% reduction of relative risk, usually translating in 5% reduction of absolute risk. The risk difference we intend to identify is consequently highly clinically relevant. Yet, even if this effect size is large, it appears congruous with the strong preclinical and clinical evidence we provide.

The annual incidence of AMI (Acute Myocardial Infarction) is estimated at 100–150 per 100,000 inhabitants in France and 5-8% of AMI patients will develop cardiogenic shock. Therefore, the annual

incidence for cardiogenic shock following MI is 12 per 100,000 inhabitants. It was recently found that cardiogenic shock was secondary to AMI in 68 % [21]. Interestingly, in this study, post cardiac surgery cardiogenic shock patients were not included. Therefore, the annual incidence of all causes of CS might be estimated at 18-20 per 100,000 inhabitants (including MI, myocarditis, cardiomyopathy and shock post cardiac surgery) in France with a mortality rate of 50 %.

Reducing the death rate by 15% would save up to 1860 lives in France. This decrease in death rate might be accompanied by a reduction in the duration of ICU and hospital stays, therefore reducing the costs associated with the care of these critically ill patients. Better long-term outcomes might also be expected.

This issue is important because ECMO use during CS management is still increasing worldwide and it is now urgent to determine the best approach to optimize such promising therapy. Recent papers demonstrated that the use of ECMO has increased rapidly, whereas rates of in-hospital mortality have decreased. These changes have taken place in the context of declining hospital costs associated with ECMO.

Finally, lessons from the SHOCK study [22] demonstrate that an efficient treatment of cardiogenic shock may be associated with a delay improvement in mortality. In the SHOCK study, emergency revascularization did not significantly reduce overall mortality at 30 days. However, after six months there was a significant survival benefit. Therefore, we will also study the effects of moderate hypothermia on mortality at 180 days.

1.4.2 **Risks**

The induction of moderate hypothermia induces numerous changes throughout the body. The most important physiological changes and side effects, and their consequences for patient management, are discussed below.

Moderate hypothermia is/might be associated with shivering, modifications in blood gas management, hyperglycemia, electrocardiographic changes, mild coagulopathy and increased sensitivity to infection [5].

Since moderate hypothermia is widely used for resuscitated patients after cardiac arrest, strategies have been developed to minimize these potential side effects. Finally, moderate hypothermia was used for patients with resuscitated cardiac arrest treated with ECMO and none particular side effects have been described [23].

Management of physiological effects of hypothermia based on the literature [5]:

- a) The tolerance to hypothermia will be ensured with the cautious use of sedation and eventually with the use of a paralyzing agent in cases of shivering. Use of a developed shivering assessment scale will be proposed for this purpose [23].
- b) Management of blood gas: Blood gas values are temperature dependent, and if blood gas are warmed to 37°C before analysis (as is common in most laboratories), Po₂ and Pco₂ will be overestimated and pH underestimated in hypothermic patients. For accurate temperature correction, blood gas will be analyzed at the patient's real temperature.

- c) Glycemia management: Hypothermia can also decrease insulin sensitivity and the amounts of insulin secreted by the pancreas. This can lead to hyperglycemia and/or an increase in the doses of insulin required to maintain glucose levels within target range. Prevention and/or prompt correction of severe hyperglycemia will be part of the therapeutic strategy during hypothermia treatment. Furthermore, it should be realized that doses of insulin required to maintain normoglycemia are likely to decrease when the patient is rewarmed; this means that hypoglycemia can easily develop in the rewarming phase as insulin sensitivity is restored, particularly if the patient is rewarmed (too) quickly.
- d) Coagulation: Very mild hypothermia (35°C) does not affect coagulation, and can be safely used even if bleeding risks are high. Temperatures of 33°C to 35°C affect platelet function only; if surgical procedures are performed under hypothermic conditions, platelet transfusion may be considered. Coagulation factors other than platelet function are affected only when temperatures decrease below 33°C.

In normothermia group, no additional risk linked to research is expected.

1.4.3 Benefits/risks balance

The hypothermia side effects are well known. Strategies described above allow to minimizing these potential side effects. No severe side effects associated have been described in previous studies especially when compared to the high severity of CS patients treated with ECMO. Therefore potential benefits/risks balance is clearly positive in this study.

1.5 ORIGINALITY AND INNOVATIVE ASPECTS

The study is original since despite very suggestive pre-clinical and clinical proof of concepts, there is only one ongoing study in CS patients non-treated with VA-ECMO (NCT01890317) and **no reported study regarding the use of hypothermia during CS treated with VA-ECMO**.

Moreover, hypothermia induction during VA-ECMO does not require any additional device or supplementary catheter insertion since body temperature is easily controlled with the circuit heat controller which is available in all potential centers

This issue is important because VA-ECMO use during CS management is still increasing worldwide and it is now urgent to determine the best approach to optimize such promising therapy. Recent papers demonstrated that the use of VA-ECMO has increased rapidly, whereas rates of in-hospital mortality have decreased. These changes have taken place in the context of declining hospital costs associated with VA-ECMO. Finally, comparatively to drug/new device research, hypothermia is inexpensive and very simple to implement in real life. Therefore, the only cost for society will be the grant for the study.

3 STUDY OBJECTIVES

In this chapter, and accordingly to the literature, moderate hypothermia is definite as a temperature between $33^{\circ}C \le T^{\circ}C \le 34^{\circ}C$. Normothermia is definite as a temperature at $36^{\circ}C \le T^{\circ}C \le 37^{\circ}C$.

3.1 PRIMARY OBJECTIVE

The study objective is to determine whether early moderate hypothermia $(33^{\circ}C \le T^{\circ}C \le 34^{\circ}C)$ is superior to normothermia $36^{\circ}C \le T^{\circ}C \le 37^{\circ}C$ in patients with cardiogenic shock treated with VA-ECMO with respect to 30-day mortality.

3.2 SECONDARY OBJECTIVES

Evaluation of the impact of moderate hypothermia on:

- Mortality during hospitalization and up to 180 days
- VA-ECMO weaning time
- Adverse cardiovascular events
- Necessity of fluid and vasopressor (norepinephrine, epinephrine)
- Lactate clearance
- Duration of organ failure
- Mechanical ventilation support use
- Renal replacement therapy use
- Duration of ICU stay and total duration of hospitalization
- The risk of bleeding
- The risk of Sepsis (pulmonary, blood, venous lines, VA-ECMO cannulaes)

3.3 STUDY OUCOME MEASURES

3.3.1 **Primary endpoints**

All-cause mortality at day 30 following randomization (i.e. 30 day mortality)

3.3.2 **Secondary endpoints:**

[figure not shown]
- All-cause mortality at 48 hours and day 7, 60, 180
- VA-ECMO duration
- Composite endpoint of death, cardiac transplant, escalation to LVAD, stroke at days 30, 60, 180
- Cumulated amount of administered fluids and duration of vasopressors use in ICU
- Duration to normalization of lactate
- Number of days alive without organ failure(s), defined with the SOFA score and its components (respiratory, liver, coagulation and renal), between inclusion, D7 and D30
- Duration of mechanical ventilation and the number of days between inclusion and day 30/ day 60/ day 180, alive without mechanical ventilation
- Number of days alive without renal replacement therapy, and the number of days, between inclusion and day 30, day 60 and day 180, without renal replacement therapy

- Duration of ICU stay, of hospitalization
- Number of severe and moderate bleeding complications (GUSTO-definition, N Engl J Med. 1993;329:673–682) and the number of packed red blood cells transfused under VA-ECMO
- Infection probability: pulmonary, blood and VA-ECMO cannulaes

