4.1.4 Inclusion and randomization of patient

The inclusion and randomization of the patient will be performed after VA-ECMO indication and implementation. Inclusion and study intervention will be performed as soon as possible **during the first 6 hours (preferably 4 hours) after VA-ECMO initiation.**

After eligibility verification, complete clinical examination and inform consent process (cf chapter 13.2), patient will be randomized. The patients will be placed on moderate hypothermia ($33^{\circ}C \le T^{\circ}C \le 34^{\circ}C$) or maintained on normothermia $36^{\circ}C \le T^{\circ}C \le 37^{\circ}C$ during 24 hours ± 1h according to the group.

Data collected (nonspecific to the study) at inclusion and during ICU stay after randomization : demographic data, medical history, SOFA score, biological data (Arterial Lactate, ASAT, ALAT, urea, creatinine, coagulation parameters..), amount of paralyzing agent and sedative, amount of insulin...), concomitant drugs, treatments (fluid amount, vasopressors, inotropes, echocardiography at inclusion performed before study intervention (echocardiography data result from usual care...))...

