4.3 BIAS CONSIDERATION

4.3.1 Randomization procedure

Randomization will be performed after enrolment using a centralized on-line randomization system (Cleanweb[™]) available 24h/24h.

Treatments arms :

- **Experimental group:** Patients with CS allocated to a strategy of moderate hypothermia (33°C≤ T°C ≤34°C) associated with usual care.
- Control group: Patients with CS allocated to a strategy of normothermia 36°C≤ T°C ≤37°C associated with usual care.

Randomization will be stratified on the center. The randomization plan will be devised by Centre investigation Clinique 1433 module Plurithématique de Nancy, France.

4.3.2 **Replacement procedures for patients**

All patients non randomized will be replaced to reach 334 patients (167 patients in each group) (cf chapter 11.8)

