11.1.2 Statistical analysis for the secondary endpoints

For the secondary analysis of a) all-cause mortality at 48 hours and day 7, 60, 180, b) the composite endpoint of death, cardiac transplant, escalation to LVAD, stroke at days 30, 60, 180 the same analysis strategy will be performed as for the primary endpoint.

Unpaired t-test will be performed, after checking for normality of the variable's distribution, for the outcomes mentioned below. Importantly, In case of non-normal distributions (which is highly likely for all duration data), non-parametric tests will be performed.

- VA-ECMO duration
- cumulated amount of administered fluids and duration of vasopressors use
- duration to normalization of lactate
- Number of days alive without organ failure(s), defined with the SOFA score and its components (respiratory, liver, coagulation and renal), between inclusion, D7 and D30
- duration of mechanical ventilation and the number of days, between inclusion and day 30/ day 60/ day 180, alive without a mechanical ventilation
- number of days alive without renal replacement therapy, and the number of days, between inclusion and day 30/ day 60/ day 180, without renal replacement therapy
- duration of ICU stay, of hospitalization
- number of severe and moderate bleeding complications (gusto-definition) and number of packed red blood cells transfused under VA-ECMO

Chi-square tests (or Fisher exact test in case of insufficient number of expected patients in on of the 2x2 cell) will be performed for the outcomes mentioned below:

- Pulmonary, blood and VA-ECMO cannulaes infections

To illustrate the association, an odd-ratio will be provided.

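### Time to lactate normalization is compared without adjusting for inclusion lactate, which is collected; this gives up some precision but causes no bias

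*Protocol*

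**What the plan says.** Section 3.2 lists "Lactate clearance" among the secondary objectives. The only lactate endpoint in section 3.3.2 is "Duration to normalization of lactate".

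Section 11.1.2 places "duration to normalization of lactate" in a list of outcomes with a common method: "Unpaired t-test will be performed, after checking for normality of the variable's distribution, for the outcomes mentioned below". It then adds: "In case of non-normal distributions (which is highly likely for all duration data), non-parametric tests will be performed". No covariate is named for any outcome in that list.

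Section 4.1.4 lists the data collected at inclusion and during the ICU stay, among them "biological data (Arterial Lactate, ASAT, ALAT, urea, creatinine, coagulation parameters". Section 4.3.1 states "Randomization will be stratified on the center", so inclusion lactate is not balanced by design. Sections 5.3 and 5.4 contain no lactate criterion, and section 4.1.4 allows inclusion up to 6 hours after VA-ECMO initiation. Some patients may therefore be normal already when they are randomized. Section 11.8 includes every randomized patient in the analysis.

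**The concern.** Time to a fixed normal value mixes two things: how fast lactate falls, which hypothermia might change, and how high it was at the start, which hypothermia cannot change. A two-group test without the starting value treats spread in starting lactate as noise. A patient already normal at inclusion can show no effect of treatment on this endpoint.

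What is at stake is the chance of seeing a real effect on lactate in a secondary analysis that bears on the trial's organ-protection hypothesis. The covariate that would recover part of the loss is already on the data list.

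**Working it through.** **1. The plan's own figure.** The protocol states no power for lactate. The sample size it does state, 167 per group for 30-day mortality (50% versus 35%, 80% power, two-sided 5%), reproduces with unpooled variance: n = (1.960 + 0.842)² × (0.50×0.50 + 0.35×0.65) / 0.15² = 7.849 × 0.4775 / 0.0225 = 166.6, so 167. I carry 167 per arm forward, with the final two-sided level of 0.049 from section 11.3.

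**2. Dependence on the starting level.** Under first-order decay with normal at 2 mmol/L (both assumed), time = half-life × log2(L0/2), where L0 is the starting lactate. At 4 mmol/L this is 1 half-life and at 8 mmol/L it is 2. At identical clearance the second patient takes twice as long.

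**3. Loss as a function of correlation.** Let r be the correlation between inclusion lactate and time to normalization. The documents give no value for it. Adjustment multiplies the residual SD by √(1 − r²). If the adjusted analysis has 80% power, the unadjusted power is Φ[(1.969 + 0.842) × √(1 − r²) − 1.969]. For r = 0.6: 2.810 × 0.8 − 1.969 = 0.280, and Φ = 61%.

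| r | Unadjusted power | Loss (points) |
|---|---|---|
| 0.2 | 78% | 2 |
| 0.3 | 76% | 4 |
| 0.4 | 73% | 7 |
| 0.5 | 68% | 12 |
| 0.6 | 61% | 19 |
| 0.7 | 52% | 28 |
| 0.8 | 39% | 41 |

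The loss is small up to about r = 0.4 and large only from about 0.7.

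**4. Simulation with patients who never normalize.** All of these inputs are assumptions: inclusion lactate lognormal with median 5 mmol/L; normal at 2 mmol/L; half-life lognormal with median 10 h and log-SD 0.65; sampling every 4 hours; patients who never normalize ranked worst; half-life 25% shorter under hypothermia; 167 per arm. The planned test is taken as a two-sample rank test. The adjusted test is rank ANCOVA on inclusion lactate in all patients.

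| Lactate log-SD | Never normalize | Planned | Adjusted |
|---|---|---|---|
| 0.7 | 20% | 29% | 40% |
| 0.4 | 20% | 48% | 56% |
| 0.7 | 40% | 13% | 14% |
| 0.7 | 50% | 8% | 9% |

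I repeated this model and the results agreed within simulation error. With no treatment effect, rejection was 5.2% for the planned test and 5.4% for the adjusted one, which fits the nominal 4.9%.

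**5. Adjusting versus excluding.** In the first row, also dropping patients already normal at inclusion moves power only from 40% to 43%. In another setting (median 4 mmol/L, half-life log-SD 0.8) power was 16% as planned, 25% with exclusion alone, 25% with the covariate alone and 28% with both. Adjustment in all patients therefore gives most of the gain, and no randomized patient has to be dropped.

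**The case against.** **It belongs in the analysis plan.** Covariates are often settled there, and section 11.1.2 does not name the non-parametric test, so rank ANCOVA could be said to fit its wording. This stands in part. The point is therefore not that detail is missing. The protocol does assign this endpoint a method, an unpaired test or a non-parametric counterpart, and that method can be improved at almost no cost.

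**Objective and endpoint contradict each other.** A reader might infer this, because clearance is a rate and the endpoint is a time. The documents do not support it as an error. Section 3.2 is a list of short topics, and section 3.3.2 makes each of them measurable; weaning time, for example, becomes VA-ECMO duration. Time to normalization can be read as doing the same for lactate.

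**Starting lactate strongly determines the result and most of the power is lost.** This too is tempting, and some settings show a large loss. But the documents give no lactate distribution, half-life or correlation, and other plausible settings show almost none. Section 11.2 assumes 50% mortality in the control group. Some patients will normalize before dying, so 50% never normalizing is an upper illustration, but the rows with little gain cannot be set aside.

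**Chance imbalance would pass for a treatment effect.** Randomization balances inclusion lactate on average, and the type I error already allows for chance imbalance. This is a matter of precision, not bias.

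**Conclusion.** The point holds as a low-priority improvement. Section 11.1.2 analyses time to lactate normalization without a collected baseline value on which that time depends by construction, and so gives up some precision. The test remains valid, the endpoint is secondary with no stated power, and the conclusion on 30-day mortality is untouched.

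The size rests on assumptions that the documents neither give nor rule out. For a 25% shorter half-life, the gain is about 8 to 11 percentage points when 20% never normalize (48% to 56%, 29% to 40%) and about 1 point when 40% to 50% never normalize. Even with adjustment, power stays at or below 56% in these settings, so a non-significant lactate result would remain weak evidence of no effect.

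**What to change.** In section 11.1.2, take time to lactate normalization out of the common unadjusted list. Compare it in all randomized patients, in line with section 11.8, adjusted for the last arterial lactate before randomization. Either rank ANCOVA or a time-to-event model with log inclusion lactate would serve; name one in advance. The value must precede randomization, because section 4.1.4 covers samples from inclusion and from the later ICU stay together.

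As a supportive analysis, repeat the comparison in patients whose pre-randomization lactate was above normal, and report by arm how many were already normal. This subset should not be the main analysis, since it departs from section 11.8 and adds little once the covariate is in.

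The cost is a change of wording and slightly more analysis work. Arterial lactate is already on the list of data collected at inclusion.
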